Medication: Solriamfetol (SRFTL) or placebo (PLA) will be administered at 2pm daily for 4 weeks. Dosage will (for all subjects) start at 75mg. This dosage was chosen through weighing up the need to extend wake/delay bedtime to consolidate sleep and improve sleep continuity (necessitating a later timing of dose than typical), without inadvertently enhancing wake to the point where it extends sleep latency. Rather than downwardly titrate the medication, the timing of dosing will be altered where required (for example, timing advanced to 1pm or 12pm). Changes in dose timing will occur when the study staff (therapist, PI, and medical collaborator) deem it to be optimal (i.e., in response to extended sleep latency). Subjects in the SRFT + CBT-I arm will also be eligible for changes in dose timing if they report being unable to adhere to the prescribed time to bed (PTTB) component of CBT-I. As noted above, medication use will also include a 1-week placebo run-in and a 3-week placebo “run-out” (eight weeks’ total). The timing of the first administration of SRFTL will (for those receiving CBT-I) align with the start of sleep restriction (Session 2).

All study medication will be provided by Axsome Pharmaceuticals (no cost) and will be received, stored, and packaged by the University of Pennsylvania Investigational Drug Service (IDS). DS will create blister packs for each patient that are identical and will allocate active medication and placebo according to treatment condition. This will enable double blinding of the study. All doses will be over-encapsulated, and all daily doses will be delivered as a single capsule. The use of blister packs will also allow us to not only track adherence but to identify the patterning of medication use.

Cognitive Behavioral Therapy: Treatment will be conducted by a master therapist via a HIPAA compliant video link (Zoom), with 1-2 members of our established cohort of CBT-I experts (n=17) serving as backup therapists. Sessions 1-8 will follow our published protocol (published in 2005 by Springer). Each session will be conducted individually and have a singular focus per session. All sessions following the delivery of sleep restriction therapy & stimulus control instructions (post Session 2) will include, as needed, management of non-adherence and/or time-in-bed titration. The Session specific itinerary will be as follows.

Session 1: evaluation and orientation

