Session 2: data acquisition and delivery of sleep restriction therapy & stimulus control instructions

Session 3: review of sleep hygiene

Session 4: management of non-adherence and/or time-in-bed titration only

Session 5: cognitive therapy [de-catastrophization]

Session 6: management of non-adherence and/or time-in-bed titration only

Session 7: management of non-adherence and/or time-in-bed titration only

Session 8: review of treatment progress and relapse prevention.

All treatment will be delivered by a single master therapist ([name] PhD CBSM). [name] has more than 27 years’ experience with CBT-I, he is one of the authors of our published treatment manual (1), and he is also a co-author of a second CBT-I treatment manual (2). He was a consultant for the VA’s rollout of CBT-I, he jointly conducts the Penn 3-day Basic and Advanced CBT-I courses, and he regularly conducts on-site one-day CBT-I workshops. As a final testament to his expertise, he was one of the first individuals to be certified in behavioral sleep medicine and one of the first to receive the SBSM’s Distinguished Career Achievement Award.

5. General Design

A double blind 2x2 mixed model design. The two factors will be 1) treatment (+/- solriamfetol and +/- CBT-I) and 2) Time (pre-post assessment, with additional follow-up data). Patients with insomnia will be randomly assigned to treatment condition.

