The study CRC will dispense and receive the foil packs. The pattern of used and unused medication will be captured by xeroxing or photographing each foil pack. Once a subject has completed their participation in the study (i.e., they have either completed the study, experienced treatment non-response or relapse, or withdrew from the study) they will be given the option to either (a) come to our office at [name] and return the blister packs to the CRC, who will bring them to IDS for destruction or (b) take the blister-packs to a local pharmacy and record a video of themselves placing the blister-packs in a safe drug disposal box, and share the video with study staff. This can be done via email or by uploading the video via REDCap (see example link: <https://redcap.med.upenn.edu/surveys/?s=XE4T3MKRTPNL7JY7>). The video will not include the subject's face or other identifying information. This will ensure that the medication is properly disposed of, and that this disposal is documented. Note: the study's informed consent already mentions that we cannot guarantee the security of email correspondence, and that email privacy is based on the email provider's user agreement. We will remind subjects of this so they can consider this factor when deciding whether to return the medication to our office (no video required) or to their local pharmacy's drug disposal box (video required).

h. Subject Compliance Monitoring

Pill use will be tracked per week via the sleep diary. These data will be compared to, and corroborated with, the foil pack data.

i. Return or Destruction of Investigational Product

Blister packs will be returned once the subject has completed the study. Following the archiving of the pill pack (pill utilization pattern captured by xeroxing or photograph) the study CRC will return the foil packs and remaining capsules to Investigational Drug Services of the University of Pennsylvania for destruction.

8. Study Procedures

All subjects will receive medication and complete daily sleep diaries and weekly questionnaires.

Does your study use MRI? (CAMRIS is the appropriate contact for all studies involving MRIs)

Yes No

Check of all that apply:

1.5T MRI
 3T MRI
 7TMRI

Does the MRI use investigational sequences and/or coils?

(See Experimental Device Clause)

Yes No Unsure

Does your study include pregnant women?

(See Pregnancy Clause and Justification)

Yes No

Does the MRI require the use of Contrast Agents?

(See Contrast Risks)

Yes No

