As noted above, side effects will be assessed in several ways: daily assessments via the sleep diaries and weekly evaluation with a medical symptom checklist (52 symptoms where positive endorsements allow subjects to rate their average severity and number of days affected).

10. Statistical Plan

k. Primary Endpoint

The primary endpoint is total wake time (time spent awake in bed) at the end of post-treatment, as measured via a web based self-report Sleep Diary.

I. Secondary Endpoints

1. Patients treated with CBT-I will have significantly greater improvements in sleep continuity from baseline to post-treatment compared to patients not administered CBT-I.
2. Patients treated with CBT-I in combination with solriamfetol will have significantly greater improvements in sleep continuity from baseline to post-treatment compared to patients treated with CBT-I alone.
3. Exploratory hypotheses: Patients treated with CBT-I in combination with solriamfetol will have significantly greater adherence with sleep restriction (i.e., sleep rescheduling, prescribed time to bed [PTTB]) and on daytime performance measures (e.g., ESS, FSS, etc.) compared to CBT-I alone.

m. Sample Size and Power Determination

To detect a clinically significant difference in self-reported total wake time of 30 minutes between the four treatment groups at the end of post-treatment using an ANOVA test, this study will require 10 subjects per group x 4 groups = 40 treatment completers. These calculations assume a standard deviation in total wake time of 19 minutes, with 80% power to detect the clinically significant change at an alpha level of .05. A total of 60 subjects will be recruited to obtain a sample of 40 subjects that complete the study due to attrition.

n. Statistical Methods

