Primary analyses will be conducted on an intention to treat basis and the trial conducted and reported according to CONSORT guidelines. Variable distributions will be examined to investigate homoscedasticity, outliers and normality, and corrected where appropriate using data transformations. The primary analysis is a 4(condition: +/- solriamfetol and +/- CBT-I) x 2(time: pre- and post-treatment) mixed ANOVA on absolute and percent change in total wake time ([TWT], time spent awake per night). If the interaction between condition and time is significant, Dunnett multiple comparisons will be conducted to further investigate differences in TWT between active treatment conditions versus the control condition to test Hypotheses 1-3. These analyses will be unadjusted in the first instance and then adjusted for covariates (primarily, age and sex).

An interim unadjusted analysis as per above will be conducted after 50% of the target sample have completed post-treatment (i.e., when N=20).

Secondary analyses include examining the interaction between treatment condition and time on other outcomes, including sleep continuity assessed via Sleep Diary (SL, WASO, EMA, TST, SE), insomnia (ISI), daytime sleepiness (ESS and KSS), fatigue (FSS and modified KSS), and daytime function (FOSQ-10, POMS, and PVT). Additionally, compliance to the medication (adherence to daily pill administration, as assessed via blister packs) and to sleep restriction (adherence to prescribed time to bed) will be investigated as covariates.

i. Baseline Data

Baseline and demographic characteristics will be summarized by standard descriptive statistics (including mean and standard deviation for continuous variables such as age and standard percentages for categorical variables such as gender).

ii. Pharmacokinetic Analysis **N/A**

iii. Interim Analysis **N/A**

iv. Safety Analysis

Side effects and adverse events will be assessed in several ways: daily assessments via the sleep diaries, and with a weekly evaluation using a medical symptoms checklist (52 symptoms where positive endorsements allow subjects to rate their average severity and number of days affected),

An adverse event will be defined as 1) any behavioral or health complaint spontaneously reported during the study, 2) an above threshold score on the study clinical assessment instruments (ESS, PHQ-9, or GAD-7), and/or a 20% increase in the medical symptom check list scores (frequency or severity).

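### Adherence to the prescribed time to bed is planned as a covariate, although it exists only in the CBT-I arms and is itself expected to respond to solriamfetol; pill adherence carries only the general risk of a post-randomisation covariate

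*Combined protocol and SAP*

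**What the plan says.** All references are to the combined protocol and SAP.

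- **Covariates.** Section 10.n (Statistical Methods) lists the secondary outcomes, to be tested for a condition-by-time interaction. It then adds that compliance with the capsules, read from the blister packs, and compliance "to sleep restriction (adherence to prescribed time to bed) will be investigated as covariates". It does not say which models receive these covariates, which arms enter, or how the second variable is coded in subjects who have no prescription.
- **Where the second variable exists.** Section 4 (Investigational Plan) allows a change of dose timing in the combination arm for subjects "unable to adhere to the prescribed time to bed (PTTB) component of CBT-I". The same section gives the starting point in the therapy schedule: "Session 2: data acquisition and delivery of sleep restriction therapy & stimulus control instructions". No time to bed is prescribed in the two arms without CBT-I.
- **Its other role.** The exploratory hypothesis in Section 5.6.2, repeated under the secondary endpoints in Section 10, is that subjects given CBT-I plus solriamfetol "will have significantly greater adherence with sleep restriction" than subjects given CBT-I alone.
- **Capsules.** Section 8 (Study Procedures) states: "All subjects will receive medication and complete daily sleep diaries and weekly questionnaires". Pill adherence therefore has a value in all four arms.
- **Primary analysis.** Section 10.n makes it intention to treat, first unadjusted and then adjusted mainly for age and sex.

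**The concern.** A covariate in a model of a randomised effect should be fixed before treatment can influence it. Neither adherence variable is. For time-to-bed adherence there are two further problems.

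1. It is undefined in half the trial, so a model that includes it cannot compare all four conditions unless some value is invented for the arms without CBT-I.
2. The plan treats it as an outcome that solriamfetol should improve. Holding it constant takes out part of the effect under study. It also compares subjects with equal adherence who reached it under different treatments, so anything that drives both adherence and sleep becomes a confounder. Because poor adherence can trigger a change of dose timing in the combination arm, adherence also feeds back into how treatment is delivered.

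Most exposed is the comparison of the combination with CBT-I alone (secondary hypothesis 2). An adjusted estimate could be printed beside the intention-to-treat result with nothing to mark it as a different quantity.

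**Working it through.** **Inputs.** From Section 10.m: a difference of 30 minutes in total wake time, SD 19 minutes, alpha 0.05, 80% power, and 10 completers per group in 4 groups. The share of any effect mediated by adherence, and the size of the drug's effect on adherence, are not in the documents and are assumed below.

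**1. The plan's own figure.** Take a one-way ANOVA with the extreme means 30 minutes apart and the other two at the midpoint. The noncentrality is n × (15² + 15²) / 19² = n × 450 / 361. For n = 10 it is 12.47, which gives power 0.811. For n = 9 it is 11.22, which gives 0.758. Ten per group is the smallest number that reaches 80%, so the plan's 40 completers reproduce.

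**2. Complete cases with time-to-bed adherence in the model.** Values exist for 2 arms × 10 = 20 of 40 completers. A design with an intercept, three condition terms and the covariate has 5 columns, but on these 20 subjects its rank is 3. No contrast with control can be estimated. Only the combination versus CBT-I alone remains, 10 against 10.

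The comparison of solriamfetol with placebo shrinks from 20 v 20 to 10 v 10. The difference detectable with 80% power (normal approximation) is 19 × √(2/n) × (1.960 + 0.842):

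| Subjects per side | Detectable difference |
|---|---|
| 20 | 16.8 min |
| 10 | 23.8 min |

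**3. Coding the variable as zero without CBT-I.** Let S and C indicate solriamfetol and CBT-I, and let P be adherence, set to 0 when C = 0. In Y = β0 + β1·S + β2·C + β3·S·C + γ·P all arms stay. But β2 is now the difference between a CBT-I subject with zero adherence and a control subject. It depends on where the adherence scale has its zero and is not the effect of being assigned to CBT-I. The combination versus CBT-I alone is still adjusted for P.

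**4. Attenuation in the combination versus CBT-I alone.** Let T be 1 for the combination and 0 for CBT-I alone. Write adherence as P = s·T + noise and the reduction in wake time as d·T + b·P + noise. The total effect is d + b·s and the adjusted coefficient estimates d. With m = b·s / (d + b·s) as the mediated share, the adjusted effect is total × (1 − m):

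| Mediated share (assumed) | Adjusted effect for a 30-min total |
|---|---|
| 0% | 30 × 1.00 = 30 min |
| 25% | 30 × 0.75 = 22.5 min |
| 50% | 30 × 0.50 = 15 min |

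Simulation with 10 per arm and 4,000 replicates gave averages of 30.0, 22.4 and 15.1 minutes, against an unadjusted 30. This assumes that adherence and sleep have no common cause. With one, the adjusted estimate carries a further bias that these figures do not include.

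**5. Power does not move in one direction.** Unadjusted power for 30 minutes, SD 19, 10 v 10 is 0.916 (t test). With total SD held at 19, adjusted power is about 34% if half the effect is mediated and the drug shifts adherence by 1.5 SD. It is about 96% if a quarter is mediated and the shift is 0.5 SD. It falls when the covariate is strongly tied to arm and can rise when the covariate explains much of the residual variation.

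**The case against.** The strongest reply is that nothing planned as confirmatory depends on this sentence. It closes the paragraph on secondary analyses, speaks only of investigating covariates, and follows a list of outcomes other than total wake time. The primary result is intention to treat and is reported unadjusted first. That stands.

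It is also fair that no four-arm complete-case model is written down. The time-to-bed analysis could be meant only for the CBT-I arms, where the exploratory hypothesis lies. The loss of 20 completers is thus a consequence of one natural implementation, not a stated intention. The plan is silent on the arms and the coding, and that silence is what needs repair. Restricting to the CBT-I arms cures the missing values but not the adjustment for an expected effect of treatment.

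A reader might infer that pill adherence also discards the control arm or strips out effect. The documents do not support this: every subject takes capsules, packaging is identical and blinded, and no difference in capsule adherence between arms is predicted.

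A reader might also infer that the adjusted model would report that solriamfetol adds little to CBT-I, or that it necessarily loses power. Neither follows. At 50% mediation the adjusted estimate is still 15 minutes, the unadjusted result would stand beside it, and power can move either way. The 30 minutes is, moreover, a planning difference across four groups for total wake time, not a stated effect of the combination over CBT-I alone, and no planning values are given for the other outcomes.

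**Conclusion.** The concern holds for time-to-bed adherence. The same variable is a hypothesised outcome of treatment and a covariate, and it has no value in two of the four arms. Used as a covariate in a four-condition complete-case model, it leaves 20 of 40 completers and no comparison with control. Used in the combination versus CBT-I alone, it removes the mediated share of the effect, provided that better adherence lowers wake time. The size of that share cannot be derived from the documents, so the 22- and 15-minute figures are illustrations only.

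For pill adherence the concern is limited to the general risk of bias from conditioning on something measured after randomisation. It would be wrong to conclude that the trial's main result is compromised: the unadjusted intention-to-treat primary analysis is untouched. The change should be made because it is cheap and prevents a non-randomised estimate from being read as a treatment effect.

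**What to change.** Replace the covariate sentence in Section 10.n with wording to this effect:

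- Neither adherence variable enters any model that estimates a randomised treatment effect.
- Pill adherence is analysed as an outcome in all four arms.
- Time-to-bed adherence is analysed as an outcome in the two CBT-I arms only. This also supplies an explicit analysis for the exploratory hypothesis in Section 5.6.2, which Section 10.n does not now give.
- Any adherence-response or mediation analysis of time to bed is confined to the CBT-I arms, states its assumptions, and is labelled exploratory and non-randomised.

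The cost is a short change of wording and the loss of an exploratory adjusted model. Sample size and data collection stay as they are, and all 40 planned completers and all four arms remain in the treatment comparisons.

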	Inclusion Criteria. Adults ≥ 25 and ≤ 65 years of age with chronic insomnia who meet DSM-5 criteria for Insomnia Disorder and ICSD-3 criteria for Psychophysiological insomnia. In addition, all subjects will have a sleep initiation and/or a sleep maintenance complaint (≥ 30 min. to fall asleep and/or ≥ 30 min. of wakefulness during the night) with a problem frequency ≥ 3 nights/wk and problem duration ≥ 3 mo. This profile must be evident at both intake (based on retrospective reports) and as an average profile from the two weeks of baseline diaries (based on prospective sampling).
	Exclusion Criteria for All Subjects. In brief, the exclusionary criteria are currently in treatment for insomnia, unstable medical or psychiatric illness, night shift work, and/or a history of other sleep disorders.
Investigational Product (drug, biologic, device, etc.)	Solriamfetol (trade name: Sunosi), 75mg.
Duration of administration (if applicable)	4 weeks
Reference therapy	Cognitive Behavioral Therapy for Insomnia (CBT-I)
Statistical Methodology	A 2x2 mixed model design. The two factors will be 1) treatment (+/- solriamfetol and +/- CBT-I) and 2) Time (pre-post assessment, with additional follow-up data).
Safety Evaluations	Daily diary assessments of side effects, weekly symptom checklists to monitor the health status of subjects (upon disbursement of medication). We will utilize a side-effect check list based on the package insert for Solriamfetol.
Data and Safety Monitoring Plan	We will establish a four-person advisory board comprised of a second MD sleep medicine specialist, a clinical psychologist, a nurse sleep scientist, and a biostatistician. Membership consists of persons completely independent of the investigators who have no financial, scientific, or other conflicts of interest with the trial. Collaborators of the PIs will not be eligible to serve on the advisory board. The board will receive reports from the study team every six months with information about the progress of recruitment, the demographic characteristics of participants, serious adverse events, the number of dropouts, and participants' reasons for dropping out, and any protocol amendments. These meetings will focus on the conduct and progress of the study, including participant accrual, protocol compliance, and problems encountered.

BACKGROUND AND STUDY RATIONALE

1. Introduction

Background and Relevant Literature

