o. Subject Population(s) for Analysis

- All-randomized population.
- All-treated population
- Protocol-compliant population

11. Safety and Adverse Events (as stated in the IRB template)

p. Definitions

i. Adverse Event

An adverse event (AE) is any symptom, sign, illness or experience that develops or worsens in severity during the course of the study. Illnesses or injuries will be regarded as adverse events. Abnormal results of diagnostic procedures are considered to be adverse events if the abnormality:

- results in study withdrawal
- is associated with a serious adverse event
- is associated with clinical signs or symptoms
- leads to additional treatment or to further diagnostic tests
- is considered by the investigator to be of clinical significance

ii. Serious Adverse Event

Serious Adverse Event

Adverse events are classified as serious or non-serious. A serious adverse event is any AE that is:

- fatal
- life-threatening
- requires or prolongs hospital stay
- results in persistent or significant disability or incapacity
- a congenital anomaly or birth defect
- an important medical event

Important medical events are those that may not be immediately life threatening but are clearly of major clinical significance. They may jeopardize the subject and may require intervention to prevent one of the other serious outcomes noted above. For example, drug overdose or abuse, a seizure that did not result in in-patient hospitalization, or intensive treatment of bronchospasm in an emergency department would typically be considered serious.

All adverse events that do not meet any of the criteria for serious should be regarded as **non-serious adverse events**.

q. Recording of Adverse Events

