At each contact with the subject, the investigator will seek information on adverse events by specific questioning and, as appropriate, by examination. Information on all adverse events will be recorded immediately in the source document, and also in the appropriate adverse event module of the case report form (CRF). All clearly related signs, symptoms, and abnormal diagnostic procedures results will be recorded in the source document, though grouped under one diagnosis. All adverse events occurring during the study period will be recorded. The clinical course of each event will be followed until resolution, stabilization, or until it has been determined that the study intervention or participation is not the cause. Serious adverse events that are still ongoing at the end of the study period will be followed up to determine the final outcome. Any serious adverse event that occurs after the study period and is considered to be possibly related to the study intervention or study participation will be recorded and reported immediately.

r. Relationship of AE to Study

The relationship of each adverse event to the study procedures will be classified in terms of the event's potential relationship to the study (definitely related, probably related, possibly related, unlikely or unrelated).

s. Reporting of Adverse Events, Adverse Device Effects and Unanticipated Problems

The occurrence of adverse events will be reported to the study's medical collaborators, advisory board chair, Penn IRB, and our contacts at Axsome.

If the report is supplied as a narrative, the minimum necessary information to be provided at the time of the initial report includes:

- *Study identifier*
- *Study Center*
- *Subject number*
- *A description of the event*
- *Date of onset*
- *Current status*
- *Whether study intervention was discontinued*
- *The reason why the event is classified as serious*
- *Investigator assessment of the association between the event and study intervention*

Additionally all other events (unanticipated problems, adverse reactions, unanticipated adverse device effects and subject complaints) will be recorded and reported with respect to institutional and federal policies as described in the Penn Manual and below.

i. Follow-up report

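### The Safety Analysis (section 10, n.iv) defines an adverse event more narrowly than section 11, with no route for side effects found only by diary, by questioning, or by a checklist rise below 20%

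*Combined protocol and SAP*

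**What the plan says.** Section 10, n.iv (Safety Analysis) opens with the methods: "Side effects and adverse events will be assessed in several ways: daily assessments via the sleep diaries", followed by a weekly medical symptom checklist, described as "52 symptoms where positive endorsements allow subjects to rate their average severity and number of days affected". It then sets out three routes to an adverse event:

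- Route 1, volunteered complaints: "An adverse event will be defined as 1) any behavioral or health complaint spontaneously reported during the study".
- Route 2, scale scores: a value over an unstated cut-off on the ESS, PHQ-9 or GAD-7.
- Route 3, the checklist: "and/or a 20% increase in the medical symptom check list scores (frequency or severity").

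The synopsis (Safety Evaluations) lists the same two sources: "Daily diary assessments of side effects, weekly symptom checklists to monitor the health status of subjects".

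Section 11, p.i defines the term again: "An adverse event (AE) is any symptom, sign, illness or experience that develops or worsens in severity during the course of the study". Section 11, q says that at each contact "the investigator will seek information on adverse events by specific questioning and, as appropriate, by examination". It also requires every adverse event in the study period to be recorded and sends them to the adverse-event module of the case report form.

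Neither section refers to the other's definition.

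**The concern.** The plan collects side effects mainly by asking for them: every day in the diary, every week on the checklist, and by questioning at each contact. The definition placed in the Statistical Plan admits only some of what those methods yield. An analyst who follows 10.n.iv literally has no basis for counting a headache entered in the diary, or palpitations disclosed on questioning, unless a scale score or the checklist total also moves far enough.

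Subject-reported symptoms carry most of the on-treatment safety information here, because section 9 marks physical examination and vital signs as not applicable. The effects listed under Risks of Solriamfetol (headache, nausea, dizziness, palpitations and others) are of the kind that a diary item or a direct question would bring out. The protocol's own example of an adverse response, in sections 2 and 4, is delayed sleep onset after the afternoon dose. Sleep latency is a diary variable in 10.n, and the diary has no route into the 10.n.iv definition.

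**Working it through.** No figure in the plan needs reproducing. The check sets the two definitions side by side for each way in which a symptom can come to light.

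| How the symptom comes to light | Section 10, n.iv | Section 11, p.i and q |
|---|---|---|
| Volunteered by the subject | Counts (route 1) | Counts if new or worsened |
| ESS, PHQ-9 or GAD-7 above threshold | Counts (route 2); thresholds not stated | Counts if it reflects a new or worsened symptom |
| Checklist, rise of 20% or more | Counts (route 3); reference point not stated | Counts if new or worsened |
| Checklist, rise below 20% | No route | Counts if new or worsened |
| Daily diary only | No route | Counts if new or worsened |
| Disclosed only on questioning | No route | Counts if new or worsened |

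The last three rows are where 10.n.iv is the narrower rule.

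Could routes 2 and 3 pick up what those rows lose?

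- **Route 2.** The instruments are a sleepiness scale, PHQ-9 and GAD-7. The plan does not present any of them as a measure of headache, nausea or palpitations. GAD-7 is also missing from the Table of Instruments and otherwise appears only as an eligibility assessment, so the plan schedules no on-study GAD-7 score. As worded, route 2 does not require a change from baseline, so a score that was already high at entry could count. A threshold score is therefore a different quantity from a new or worsened symptom.
- **Route 3.** The plan does not say whether the 20% applies to a single item or a total, or whether it is measured from baseline or from the previous week. A percentage rise from zero is undefined. Some new endorsements will reach 20% and others may not; the documents do not allow the split to be calculated.

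Does the plan say which definition feeds the analysis? It does not. Item 10.n.iv sits in the Statistical Plan under Safety Analysis and says how an adverse event will be defined. Section 11 is headed as IRB template text and governs recording and reporting. No adverse-event table or comparison by arm is specified in either place.

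Is the opportunity to report equal across arms? Section 8 gives all subjects the daily diary and weekly questionnaires, so those two sources are scheduled identically. Volunteered and questioned reports depend on contact. CBT-I subjects have 8 weekly sessions (section 4). For the others, the documents describe monthly evaluation at blister-pack return (section 2) and contact on request (section 8, d).

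**The case against.** The strongest reply is that nothing need be lost. Section 11 defines an adverse event broadly, requires questioning, and sends every event to the case report form. If the safety table is drawn from that module, all elicited events are in it. The opening sentence of 10.n.iv also names the diary, so diary side effects are not ignored in the safety analysis; what is missing is an explicit step from a diary entry to the label of adverse event. This stands in part: loss of events is possible but not shown. It does not remove the conflict, because the Statistical Plan's own definition differs and nothing ranks one above the other.

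Two stronger readings should be resisted.

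- A reader might infer that 10.n.iv counts only volunteered complaints, so that all elicited side effects drop out. The same sentence goes on to count scale scores and checklist rises, and both are elicited.
- A reader might infer from the rates under Risks of Solriamfetol (headache up to 5%, other effects below 2%) that so few drug-caused events are expected that the wording would make the drug's harms vanish. Those rates are placebo-adjusted and leave out background events, so they are not the number of reports at stake. The plan also does not say how reports divide between volunteered and elicited.

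A fair caution about any remedy is that questioning takes place at each contact and CBT-I subjects have more contacts. Counting questioned events could raise totals in the CBT-I arms for reasons unrelated to harm. This is why source needs to be shown.

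**Conclusion.** The point holds as a conflict between two stated definitions, one of which would undercount if followed. For elicited symptoms, 10.n.iv is narrower than 11.p.i: diary-only reports, questioning-only reports and checklist endorsements below the 20% rise have no route. The plan does not say which definition is analysed.

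The size cannot be expressed as a number. At one end, if the analysis uses section 11 and its case report form module, no events are lost. At the other, if it uses 10.n.iv as written, all events in those three categories are left out. Where between these the trial would fall depends on how subjects report and on a checklist scoring rule that the documents do not give.

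The direction by arm is also not established. With the drug blinded, it is reasonable to assume that a similar share of reports would be omitted on drug and placebo at the same level of CBT-I; absolute differences between drug and placebo would then shrink. Comparisons between arms with and without CBT-I are less secure, because volunteered reports may rise with contact.

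**What to change.** In section 10, n.iv, replace the whole three-route definition with that of section 11, p.i: any new or worsened symptom, whether volunteered, disclosed on questioning, or entered in the diary or checklist. Replacing route 1 alone would leave the 20% rule overlapping with the broader definition.

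Report above-threshold ESS, PHQ-9 and GAD-7 scores and the 20% checklist rise as separate safety summaries, so that they do not act as a filter on adverse events. State the thresholds, the checklist score used and the reference point for the 20%. Either schedule GAD-7 in the Table of Instruments or remove it from the safety text.

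Tabulate adverse events by arm and by source (volunteered, questioned, diary, checklist). Diary and checklist counts can be compared across all arms on an equal schedule; volunteered and questioned counts should be read with the extra CBT-I contact in mind.

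The cost is a change of wording and a source column in the adverse-event table. The revised definition uses data already planned; only scheduling GAD-7, if chosen, would add collection. The downside is a higher raw count of minor events in every arm, which the source breakdown keeps interpretable.
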